8.3.3 Reporting of Pregnancy

Pregnancies occurring in female study participants will be reported via Advantage eClinical® on the Pregnancy Report form. With the participant's permission all protocol-required venous blood samples will be obtained and the participant will continue to be followed for safety for the duration of this trial. Efforts will be made to follow all pregnancies reported during the course of this trial to pregnancy outcome pending the participant's permission.

Male participants will be asked if their female partner has become pregnant during the study and any pregnancy will be reported. The outcome of pregnancy in the female partner of male participant will be handled through contact with the male participant.

8.4 Type and Duration of Follow-up of Participants After Adverse Events

AEs/SAEs will be collected, assessed, and followed through resolution from the time of study product administration through approximately 3 months after receipt of study product.

Resolution of an AE/SAE is defined as the return to pretreatment status or stabilization of the condition with the expectation that it will remain chronic.

Follow-up procedures, evaluations, and outcomes will be recorded on the appropriate DCF.

8.5 Procedures to be Followed in the Event of Abnormal Laboratory Test Values or Abnormal Clinical Findings

The site PI or appropriate sub-investigator is responsible for recording all AE/SAEs that are observed or reported during this trial, regardless of the relationship to study product. AE/SAEs, abnormal laboratory test values, or abnormal clinical findings will be collected, assessed, documented, reported, and followed appropriately, using a local laboratory as necessary. Participants with elevated aminotransferase and/or bilirubin will be asked about recent seizures and mental health status change. In determining eligibility, refer to [Section 5.1](#) and the protocol-specific MOP.

Clinical and safety laboratory results will be graded for severity according to the CTCAE Version 5.0, November 2017 (see [Section 8.1.1.1](#)).

8.6 Halting Rules

8.6.1 Study Halting Criteria

The study will be immediately suspended, and no additional doses administered if any of the following occurs:

- Any death occurring during the study that was not the result of trauma or accident.
- Two or more participants experience an SAE, related to the study product.
- Three or more participants in each part of the trial (A or B) develop a severe, Grade 3 or higher, AE, systemic or laboratory, in the same MedDRA Low Level Term (LLT), assessed as related to the study product.

If any halting criterion is met, the study will be suspended, and a SMC *ad hoc* meeting will convene. The study will not be re-started until the SMC meets and provides its recommendation to DMID, the study sponsor.

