8.1.1.1 Adverse Events Grading

All AEs, including laboratory and clinical symptoms, will be graded for severity according to the Common Terminology Criteria for Adverse Events (CTCAE) Version 5.0, November 2017 (https://ctep.cancer.gov/protocoldevelopment/electronic_applications/ctc.htm#ctc_50), and assessed for relationship to study product. AEs characterized as intermittent require documentation of onset and duration of each episode. The start and stop date of each reported AE will be recorded on the appropriate DCF and eCRF.

Severity of Event:

- Mild (Grade 1): Asymptomatic or mild symptoms, Events require minimal or no treatment and do not interfere with the participant's daily activities.
- Moderate (Grade 2): Events result in a low level of inconvenience or concern with therapeutic measures. Moderate events may cause some interference with functioning and daily activities.
- Severe (Grade 3): Severe or medically significant but not immediately life threatening, interrupt the participant's daily activities; and may require intervention and hospitalization. Severe events are usually incapacitating.
- Life-threatening (Grade 4): Life-threatening consequences; urgent intervention indicated.

AEs characterized as intermittent require documentation of onset and duration of each episode.

Relationship to Study Product: The assessment of the AE's relationship to study product will be performed by a delegated, licensed study clinician listed on the Form FDA 1572. The assessment will be part of the documentation process. Whether the AE is related or not is not a factor in determining what is or is not reported in this trial. If there is any doubt as to whether a clinical observation is an AE, the event should be reported. In a clinical trial, the study product must always be suspect. To help assess the relationship, the following guidelines will be used:

- Related – There is a reasonable possibility that the study product caused the AE. Reasonable possibility means that there is evidence to suggest a causal relationship between the study product and the AE.
- Not Related – There is not a reasonable possibility that the administration of the study product caused the event.

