8.1.2 Serious Adverse Events

Serious Adverse Event (SAE): An AE or suspected adverse reaction is considered “serious” if, in the view of either the site PI or sponsor, it results in any of the following outcomes:

- Death,
- A life-threatening AE*,
- Inpatient hospitalization or prolongation of existing hospitalization,
- A persistent or significant incapacity or substantial disruption of the ability to conduct normal life functions, or
- A congenital anomaly/birth defect.

*An AE is considered “life-threatening” if, in the view of either the site PI or sponsor, its occurrence places the patient or participant at immediate risk of death. It does not include an AE that, had it occurred in a more severe form, might have caused death.

Important medical events that may not result in death, be life-threatening, or require hospitalizations may be considered serious when, based upon appropriate medical judgment they may jeopardize the health or safety of the patient or participant and may require medical or surgical intervention to prevent one of the outcomes listed in this definition. Examples of such medical events include allergic bronchospasm requiring intensive treatment in an emergency room or at home, blood dyscrasias or convulsions that do not result in inpatient hospitalization, or the development of drug dependency or drug abuse.

SAEs will be:

- Assessed for severity and relationship to study product and alternate etiology (if not related to study product).
- Recorded on the appropriate DCF and eCRF, and on the DMID SAE Report Form.
- Followed through resolution.
- Reviewed and evaluated by the DMID, SMC (periodic review unless related), and the IRB per reporting requirements.

At any time after the protocol follow-up period or completion of this study, if the site PI or appropriate sub-investigator becomes aware of an SAE that is suspected to be related to study product, the site PI or appropriate sub-investigator will report the event to the DMID Pharmacovigilance Group.

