8.7 Safety Oversight

8.7.1 Safety Monitoring Committee (SMC)

This study will utilize a SMC, which is an independent group of experts that advises DMID. The primary responsibility of the SMC is to monitor participant safety. The SMC is external to DMID and is composed of at least 3 voting members. The SMC will consist of members with appropriate Phase 1 study expertise to contribute to the interpretation of the data from this trial. Its activities will be delineated in a SMC charter that will describe the membership, responsibilities, and the scope and frequency of data reviews. The SMC will operate on a conflict-free basis independently of the study team. The DMID or the SMC may convene *ad hoc* meetings of the SMC according to protocol criteria or if there are concerns that arise during the study.

The SMC will review the safety data at the following milestones:

- Organizational meeting (prior to start of the study).
- After 6 participants in Group 2 (severe renal impairment and ESRD, not on dialysis) and their matching controls are enrolled and complete follow-up through Day 12 (Visit 02). This review will be completed prior to determining if Part B will be conducted and opening enrollment for Groups 3 and 4 and their matched healthy control participants.
- An *ad hoc* SMC meeting will be convened when a halting rule is met, or at the request of the investigator and/or DMID if there are safety concerns during the course of the study.
- Final Data Review Meeting: Approximately 6 to 8 months after final clinical database lock to review the cumulative unblinded safety data for this trial. The data will be provided in a standard summary format. The SMC may be asked to provide recommendations in response to questions posed by DMID.
- The DMID Medical Monitor is empowered to stop study enrollment if AEs that meet the halting criteria are reported or if any serious safety concerns arise. The DMID Medical Monitor will be responsible for reviewing SAEs in real time. The SMC will review SAEs on a regular basis and *ad hoc* during the study.

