14.3.2 Listing of Deaths, Other Serious and Significant Treatment Emergent Adverse Events

Table 27: Listing of Serious Adverse Events

[Implementation Note: This listing is included in the table shells document, as it is included in the body of the CSR. If the event is ongoing (no stop date), indicate “ongoing” for the “Duration”. If more than one reason is selected for the reason reported as an SAE, list all reasons in the column, separated by a comma. In the “If Not Related, Alternate Etiology” column, merge the 2 data fields for collecting alternate etiology, separate by a colon. If there are no comments for an event, populate ‘Comments’ row with ‘None’. Add columns for MedDRA HLT or LLT depending on halting criteria or other study needs. In the CSR, Participant ID should be USUBJID (not PATID) for purposes of de-identification. Listing should be sorted by Participant ID, Associated with Dose No., and No. of Days Post Associated Dose.]

Adverse Event	No. of Days Post Dose (Duration)	No. of Days Post Dose the Event Became Serious	Reason Reported as an SAE	Severity	Relationship to Study Treatment	If Not Related, Alternative Etiology	Participant Discontinued Due to AE	Outcome	MedDRA System Organ Class	MedDRA Preferred Term
Participant ID: Impairment Group: , AE Number:										
Comments:										
Participant ID: Impairment Group: , AE Number:										
Comments:										

Table 28: Listing of Non-Serious, Unsolicited, Moderate or Severe Adverse Events

[Implementation Note: This listing is included in the tables document, as it is included in the body of the CSR. If the event is ongoing (no stop date), indicate “ongoing” in the “Duration” column. In the “If Not Related, Alternate Etiology” column, merge the 2 data fields for collecting alternate etiology, separate by a colon. If there are no comments for an event, populate ‘Comments’ row with ‘None’. Add columns for MedDRA HLT or LLT depending on halting criteria or other study needs. In the CSR, Participant ID should be USUBJID (not PATID) for purposes of de-identification. Listing should be sorted by Participant ID, Associated with Dose No., and No. of Days Post Associated Dose.]

Adverse Event	No. of Days Post Dose (Duration)	Severity	Relationship to Study Treatment	If Not Related, Alternative Etiology	Participant Discontinued Due to AE	Outcome	MedDRA System Organ Class	MedDRA Preferred Term
Participant ID: Impairment Group: , AE Number:								
Comments:								

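### Counting related Grade 3+ events by Low Level Term lets one non-serious toxicity, if split over two such terms, affect up to 4 participants in a part before an automatic pause is certain, against 2 by Preferred Term

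*Protocol*

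**What the plan says.** Protocol section 8.6.1 has three automatic halting criteria. The first is any death not due to trauma or accident. The second is "Two or more participants experience an SAE, related to the study product", whatever the terms. The third requires at least three participants, counted within Part A or Part B, each with an event of Grade 3 or worse. It defines which events count together as follows: "AE, systemic or laboratory, in the same MedDRA Low Level Term (LLT), assessed as related to the study product". If any criterion is met, the study is suspended until the Safety Monitoring Committee (SMC) has met and made its recommendation.

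Neither document says that related LLTs are combined when participants are counted. Adverse event summaries use System Organ Class and PT (Protocol 10.5.3.1, SAP 9.3.2). The SAP listing shells in 14.3.2 (Tables 27 and 28) and 16.2.7 (Listing 9) have a PT column. They have no LLT column as drafted, but carry the instruction "Add columns for MedDRA HLT or LLT depending on halting criteria or other study needs".

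**The concern.** Criteria 1 and 2 cover deaths and serious events. A related, severe, non-serious event can trigger an automatic pause only through criterion 3. Such events exist in principle: the criterion expressly includes laboratory events, and a Grade 3 laboratory value need not involve incapacity or hospitalization. Increased transaminases are among the adverse reactions named in Protocol 2.3.1.

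If reports of one toxicity are coded to two LLTs, each LLT has its own count. Whether the pause happens then depends on which term each report received, not only on how many participants are affected. At stake are the participants not yet dosed in that part. The scheduled SMC review of Part A comes after all 12 participants have been dosed and followed to Day 12. Section 8.7.1 schedules no SMC review during Part B before the final one; beyond ongoing SAE review, any such meeting would be ad hoc.

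**Working it through.** The plan states no operating characteristics for the halting rule, so there is no figure to reproduce.

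**Inputs from the documents.** Threshold of 3 participants per part (8.6.1, read as within either part). Part A n = 12 and Part B n = 24 (Table 1).

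**Assumptions, because the documents give no values.**
- Both LLTs belong to one PT, and each affected participant is coded to one of them.
- The split is 50/50, 80/20 or 90/10 (w = 0.5, 0.8, 0.9).
- The true rate p of the related Grade 3+ toxicity is 2%, 5% or 10%.

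**Step 1: largest number affected with no trigger.** Each counted term can hold at most 3 − 1 = 2 participants. One PT gives 2. Two LLTs give 2 + 2 = 4, which is 4/12 = 33% of Part A or 4/24 = 17% of Part B. A fifth participant always triggers.

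**Step 2: chance that the LLT rule stays silent, given k affected.** P(a ≤ 2 and k − a ≤ 2), with a ~ Bin(k, w).

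| k | 50/50 | 80/20 | 90/10 |
|---|---|---|---|
| 3 | 75% | 48% | 27% |
| 4 | 37.5% | 15% | 5% |
| 5 or more | 0 | 0 | 0 |

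For k = 3 the rule is silent unless all three share a term: 1 − w³ − (1 − w)³, which is 1 − 0.125 − 0.125 = 0.75 at w = 0.5.

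**Step 3: unconditional trigger probability.** One shared term: P(X ≥ 3), X ~ Bin(n, p). Split: sum over k of P(X = k) × [1 − silent probability from step 2].

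| Part | p | One term | 50/50 | 80/20 | 90/10 |
|---|---|---|---|---|---|
| A, n = 12 | 2% | 0.15% | 0.04% | 0.08% | 0.11% |
| A | 5% | 2.0% | 0.6% | 1.1% | 1.5% |
| A | 10% | 11.1% | 3.9% | 6.7% | 8.7% |
| B, n = 24 | 2% | 1.2% | 0.3% | 0.7% | 0.9% |
| B | 5% | 11.6% | 4.2% | 7.1% | 9.2% |
| B | 10% | 43.6% | 22.1% | 31.0% | 37.0% |

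**Step 4: missed triggers at p = 5%** (one term minus split, from unrounded values).
- Part A: 0.0138, 0.0086 and 0.0048 for the 50/50, 80/20 and 90/10 splits, or 1.4 down to 0.5 percentage points.
- Part B: 0.0736, 0.0450 and 0.0244, or 7.4 down to 2.4 points.

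These are upper bounds. The rate p covers all related Grade 3+ cases of the toxicity, and cases where two participants' events are serious would be halted by criterion 2. Those cases are not removed.

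**Step 5: extra participants dosed.** Suppose dosing is one at a time and reporting is immediate. The expected number dosed is then the sum, over m = 0 to n − 1, of the probability of no trigger after m participants. At 5%, LLT counting doses 0.01 to 0.035 more participants than PT counting in Part A and 0.17 to 0.49 more in Part B.

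**The case against.** The strongest reply is that LLT is an explicit choice, that the SAP provides for it, and that the problem exists only if coding splits one toxicity in a way the documents never describe. That is right as far as it goes. The shared PT is an assumption, and nothing shows that split coding is likely. CTCAE grading ("All AEs, including laboratory and clinical symptoms, will be graded for severity according to the Common Terminology Criteria for Adverse Events") and a short fixed laboratory panel limit variation in wording.

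The exposed class is also narrow. Of Grade 3 events the protocol says "Severe events are usually incapacitating", and "A persistent or significant incapacity or substantial disruption of the ability to conduct normal life functions" makes an event serious, as does hospitalization. Many severe events would therefore count under criterion 2, where two related ones halt the study. The Medical Monitor can stop enrollment for serious safety concerns, and the investigator or DMID can ask for an ad hoc SMC meeting. On the Part A SMC review, 8.7.1 says "This review will be completed prior to determining if Part B will be conducted". Each participant receives one dose, and Part B goes ahead only if AUC rises by at least 50%. All of this stands and keeps the point small. It does not supply another automatic rule for non-serious events within a part, and neither document gives a reason for preferring LLT.

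Three stronger readings should be resisted:
- **That the protocol and SAP conflict, because summaries use PT and halting uses LLT.** They do not: the SAP note on added columns anticipates an LLT rule.
- **That the rule fails 75% of the time.** That figure assumes exactly three affected participants and an even split. At a 5% rate, three or more affected has probability 2.0% in Part A.
- **That four severe cases would go unnoticed.** Only the automatic pause is at issue; the discretionary safeguards remain.

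**Conclusion.** The point holds as a minor design improvement. As written, the automatic pause for related, severe, non-serious events can depend on the choice of LLT, and the worst case over two LLTs is 4 participants in a part against 2 by PT. The bound follows from the threshold alone, given that two LLTs can share a PT. The probabilities also rest on the assumed rates and splits.

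At rates of 5% or less the Part A rule rarely triggers under either way of counting, so the practical gain lies mainly in Part B, if it is run. PT counting reduces the dependence on coding but does not remove it, since events under different PTs would still be counted apart.

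**What to change.** In criterion 3 of Protocol 8.6.1, make the MedDRA Preferred Term the counting unit in place of the Low Level Term. Keep three participants per part, Grade 3 or higher, and related to study product. The listing shells need no added column for this, although they are final-report shells and do not govern how halting is monitored in real time.

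The edit is one phrase, but it is a protocol amendment and needs IRB approval before use (Protocol 9.1). The operating cost is a slightly higher chance of suspension and an ad hoc SMC meeting. For one toxicity at a 5% rate that is at most 1.4 percentage points in Part A and 7.4 in Part B, and it arises only when at least three participants have had the same severe, related toxicity. If an amendment is not otherwise planned, the change could wait for the next one.

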8.7 Safety Oversight

8.7.1 Safety Monitoring Committee (SMC)

This study will utilize a SMC, which is an independent group of experts that advises DMID. The primary responsibility of the SMC is to monitor participant safety. The SMC is external to DMID and is composed of at least 3 voting members. The SMC will consist of members with appropriate Phase 1 study expertise to contribute to the interpretation of the data from this trial. Its activities will be delineated in a SMC charter that will describe the membership, responsibilities, and the scope and frequency of data reviews. The SMC will operate on a conflict-free basis independently of the study team. The DMID or the SMC may convene *ad hoc* meetings of the SMC according to protocol criteria or if there are concerns that arise during the study.

The SMC will review the safety data at the following milestones:

- Organizational meeting (prior to start of the study).
- After 6 participants in Group 2 (severe renal impairment and ESRD, not on dialysis) and their matching controls are enrolled and complete follow-up through Day 12 (Visit 02). This review will be completed prior to determining if Part B will be conducted and opening enrollment for Groups 3 and 4 and their matched healthy control participants.
- An *ad hoc* SMC meeting will be convened when a halting rule is met, or at the request of the investigator and/or DMID if there are safety concerns during the course of the study.
- Final Data Review Meeting: Approximately 6 to 8 months after final clinical database lock to review the cumulative unblinded safety data for this trial. The data will be provided in a standard summary format. The SMC may be asked to provide recommendations in response to questions posed by DMID.
- The DMID Medical Monitor is empowered to stop study enrollment if AEs that meet the halting criteria are reported or if any serious safety concerns arise. The DMID Medical Monitor will be responsible for reviewing SAEs in real time. The SMC will review SAEs on a regular basis and *ad hoc* during the study.

9 HUMAN PARTICIPANT PROTECTION

9.1 Institutional Review Board

The site PI will obtain IRB approval for this protocol to be conducted at his/her research site(s) and send supporting documentation to the DMID before initiating recruitment of participants. The investigator will submit applicable information to the IRB on which it relies for the review, to conduct the review in accordance with 45 CFR 46, ICH E6 Good Clinical Practice (GCP), and as applicable, 21 CFR 56 (IRB) and 21 CFR 50 (Protection of Human Participants), other federal, state, and local regulations. The IRB must be registered with the Office for Human Research Protections (OHRP) as applicable to the research. DMID must receive the documentation that verifies IRB approval for this protocol, associated informed consent documents, and upon request any recruitment material and handouts or surveys intended for the participants, prior to recruitment and enrollment of participants.

Any amendments to the protocol or consent materials will be approved by the IRB before they are implemented. IRB review and approval will occur at least annually throughout the enrollment and follow-up of participants and may cease if annual review is no longer required by applicable regulations. The investigator will notify the IRB of deviations from the protocol and reportable SAEs, as applicable to the IRB policy.

Each institution engaged in this research will hold a current Federal Wide Assurance (FWA) issued by the OHRP for federally funded research.

The IRB/IEC will determine that adequate provisions are made for soliciting the permission of each participant.

9.2 Informed Consent Process

Informed consent is a process that is initiated prior to an individual agreeing to participate in a trial and continuing throughout the individual's trial participation. Before any study procedures are performed, informed consent will be obtained from the participant and documented. Participants will receive a concise and focused presentation of key information about the clinical trial, verbally and with a written ICF. The explanation will be organized and presented in lay terminology and language that facilitates understanding why one might or might not want to participate.

An investigator or designee will describe the protocol to potential participants face-to-face. The key information about the purpose of the study, the procedures, and experimental aspects of the study, risks and discomforts, any expected benefits to the participant, and alternative treatment will be presented first to the participant.

Participants will also receive an explanation that the trial involves research, and a detailed summary of the proposed study procedures and study interventions/products. This will include aspects of the trial that are experimental, the probability for random assignment to treatment groups, any expected benefits, all possible risks (including a statement that the particular treatment or procedure may involve risks to the participant or to the unborn child, if the participant is or may become pregnant, that are currently unforeseeable), the expected duration of the participant's participation in the trial, alternative procedures that may be available and the important potential benefits and risks of these available alternative procedures.

Participants will be informed that they will be notified in a timely manner if information becomes available that may be relevant to their willingness to continue participation in the trial. Participants will receive an explanation as to whether any compensation and any medical treatments are available if injury occurs, and, if so, what they consist of, or where further information may be obtained. Participants will be informed of the anticipated financial expenses, if any, to the participant for participating in the trial, as well as any anticipated prorated payments, if any, to the participant for participating in the trial. They will be informed of whom to contact (e.g., the investigator) for answers to any questions relating to the research project.

Information will also include the foreseeable circumstances and/or reasons under which the participant's participation in the trial may be terminated. The participants will be informed that participation is voluntary and that they are free to withdraw from the study for any reason at any time without penalty or loss of benefits to which the participant is otherwise entitled.

The extent of the confidentiality of the participants' records will be defined, and participants will be informed that applicable data protection legislation will be followed. Participants will be informed that the monitor(s), auditors(s), IRB, NIAID, and regulatory authority(ies) will be granted direct access to the participant's original medical records for verification of clinical trial procedures and/or data without violating the confidentiality of the participant, to the extent permitted by the applicable laws and regulations, and that, by signing a written ICF, the participant is authorizing such access.

Participants will be informed that records identifying the participant will be kept confidential, and, to the extent permitted by the applicable laws and/or regulations, will not be made publicly available and, if the results of the trial are published, the participant's identity will remain confidential. Participants will be informed whether private information collected from this research and/or specimens will be used for additional research, even if identifiers are removed.

Participants will be allowed sufficient time to consider participation in this research trial and have the opportunity to discuss this trial with their family, friends, or legally authorized representative, or think about it prior to agreeing to participate.

ICFs will be IRB-approved, and participants will be asked to read and review the consent form. Participants must sign the ICF prior to starting any study procedures being done specifically for this trial.

Once signed, a copy of the ICF will be given to the participant(s) for their records. The participant(s) may withdraw consent at any time throughout the course of the trial. The rights and welfare of the participant(s) will be protected by emphasizing to them that the quality of their medical care will not be adversely affected if they decline to participate in this study.

Study personnel may employ recruitment efforts prior to obtaining study consent if a patient-specific screening consent is on record or if the IRB has agreed that chart review is allowed without a fully executed screening consent. In cases where there is not a patient-specific screening consent on record, site staff may pre-screen via chart review and refer potential participants to the Research staff. Research staff would obtain written consent per the standard informed consent process before conducting protocol-specific screening activities.

New information will be communicated by the site PI to participants who consent to participate in this trial in accordance with IRB requirements. The ICF will be updated, and participants will be re-consented per IRB requirements, if necessary. Participants will be given a copy of all ICFs that they sign.

